### B7601007

Nine healthy subjects participated in study B7601007, a single dose cross-over study. During study Period 1 and Period 3, 3 subjects received placebo and 6 subjects received PF-06649751 0.75 mg. During Period 2, 3 subjects received placebo and 6 subjects received PF-06649751 0.25 mg. A total of 47 all-causality AEs were reported (7 AEs in Placebo group; 28 AEs in PF-06649751 0.75 mg Period 1; 3 AEs in PF-06649751 0.25 mg; 9 AEs in PF-06649751 0.75 mg Period 3). The most frequently reported AEs were headache (4 subjects in the placebo group, 4 subjects in PF-06649751 0.75 mg Period 1 and 1 subject in Period 3), nausea (4 subjects in PF-06649751 0.75 mg Period 1 and 2 subjects in Period 3) and hot flush (1 subject in the placebo group, 3 subjects in PF-06649751 0.75 mg Period 1 and 2 subjects in Period 3); all of these AEs were considered to be treatment-related. The majority of the AEs (39/47) were mild in severity. Eight subjects reported AEs that were moderate in severity, including nausea (1 subject), vomiting (3 subjects), fatigue (1 subject), headache (1 subject), hot flush (1 subject) and orthostatic hypotension (1 subject). All moderate AEs were reported during PF-06649751 0.75 mg Period 1; they were considered to be treatment-related and resolved by end of study. Prophylactic or concomitant use of the antiemetic trimethobenzamide hydrochloride did not reduce the incidence and severity of nausea and emesis observed in the single dose first in human (FIH) study (B7601001).

### B7601005

B7601005 was a Phase 1b, 2-period, open label, multi-center, dose escalation study of PF-06649751 in subjects with Parkinson's disease experiencing motor fluctuations and, in one of the cohorts, subjects with Parkinson's disease experiencing levodopa induced dyskinesia (LID). In Period 1 of the study, L-Dopa and placebo were administered for the evaluation of L-Dopa responsiveness. During Period 2, PF-06649751 was administered for the evaluation of the safety, tolerability and pharmacokinetics of PF-06649751. The B7601005 study included 4 completed cohorts:

- Cohort 3: 5 mg QD (n= 9 subjects).
- Cohort 4: 15 mg QD (n=11 subjects).
- Cohort 5: 15 mg QD, (n=6 subjects with levodopa-induced dyskinesia).

- Cohort 6: 25 mg QD (n=19).

Based on safety data from the multiple-ascending dose study in healthy subjects (B7601002), Cohorts 1 and 2 of the study were not conducted. Multiple ascending doses of PF-06649751 up to 25 mg QD were safe and well tolerated by subjects with Parkinson's disease, with no new safety findings.

There were no deaths reported in the study. There was 1 SAE, 6 severe AEs, and 11 permanent discontinuations due to AEs. The majority of AEs occurred during the up titration period of PF-06649751 (Period 2, Days 3-24 and follow-up) but the timing and dose level at which AEs occurred were variable. The most common AE reported in all PF-06649751 treatment groups were headache, nausea, abnormal dreams, dizziness and vomiting. The gastrointestinal disorders appeared to be dose-driven as there were more nausea and vomiting in the 15 mg QD (including LID) and 25 mg QD doses compared with the 5 mg QD dose. Most AEs in all PF-06649751 treatment groups appeared related to pace and increment of up-titration rather than maximum exposure and were generally self-limited.

Across cohorts there were no apparent trends or clinically significant changes in vital signs, ECG, physical findings, laboratory values and the Parkinson's disease diary.

#### B7601009

B7601009 (n=18) was a Phase 1b, double-blind, placebo-controlled, randomized, study to evaluate the safety, tolerability and pharmacokinetics of single ascending doses of PF-06649751 in Parkinson's disease subjects. Single doses of PF-06649751 0.75 mg, 1.5 mg, 3 mg, 6 mg, 9 mg were evaluated in the study.

Two (2) sequential cohorts were planned and were to be conducted over 3 treatment periods. Study drug or placebo was administered once during each of 3 treatment periods, with an at least 7 day study drug wash out phase between treatment periods.

Single doses of PF-06649751 up to 9 mg were safe and well tolerated by subjects with Parkinson's disease. There were no deaths, SAEs, severe AEs, discontinuations due to AEs, dose reductions or temporary discontinuation due to AEs. The most common mild to moderate AEs were headache, nausea, and vomiting. Nausea and vomiting appeared to be more common in the higher dose groups (PF-06649751 3 mg, PF-06649751 6 mg and PF-06649751 9 mg treatment groups).

There were no notable findings in clinical laboratory. There appeared to be a small dose-related increase in heart rate without consistent changes in blood pressure (BP), except for the observations of orthostatic hypotension.

There was an increase of mean QTcF values in the higher dose groups (PF-06649751 6 mg and PF-06649751 9 mg) between 2 and 8 hours post dose, but no subject had a QTcF  $\geq 500$  msec or an increase of QTcF  $\geq 60$  msec.

To date, nausea and emesis have been identified as Adverse Drug Reactions (ADR) for PF-06649751.

### 1.4.3. Pharmacokinetics

The pharmacokinetic behavior of PF-06649751 following single oral doses is characterized by rapid absorption followed by bi-phasic decline in plasma concentrations. PF-06649751 reached peak concentration at approximately 1.0 to 2.0 hours following single oral doses. Both  $C_{max}$  and  $AUC_{inf}$  increased proportionally with increasing dose from 0.25 mg to 1.5 mg. Mean  $t_{1/2}$  were 21.0 to 22.4 hours. Food did not seem to alter  $T_{max}$ , however, food modestly decreased  $AUC_{inf}$  and  $C_{max}$  by about 9% and 13%, respectively at the 0.75 mg PF-06649751 dose. Co-administration of TMB did not have a noticeable impact on PF-06649751 exposures in healthy subjects.

Increases in steady state PF-06649751 exposures following multiple oral doses appeared to be approximately dose-proportional across the B7601002 and B7601005 studies. Consistent with the observed half-life, approximately 2-fold accumulation in exposures was observed following once daily dosing. Approximately 0.2% of the dose was excreted un-changed in urine at steady state. Evaluation of PF-06649751 pharmacokinetics in healthy Japanese subjects at 1.5 mg QD dose suggest no meaningful difference between Japanese and Western subjects.

Steady state PF-06649751 exposures in Parkinson's disease patients at different doses from (study B7601005) are presented in Table 1. Average steady state PF-06649751 exposures in healthy subjects (B7601002) were approximately 65% of the values observed in Parkinson's disease patients (B7601005). However, with limited number of subjects in B7601002 (N=5) and differences in the tolerability profile across populations, these differences are considered preliminary.

**Table 1. Steady State Exposures of PF-06649751 after Multiple Dosing in Parkinson's Disease Patients with Motor Fluctuations**

Dose	$C_{max,ss}$ (ng/mL)	$T_{max}$ (hrs)	$AUC_{24,ss}$ (ng*hr/mL)
5 mg once daily (n=9)	118.5 (33)	2.0 (1.0-4.0)	2105 (35)
15 mg once daily (n=7)	325.4 (46)	4.0(2.0-12.0)	5993 (61)
25 mg once daily (n=7)	401.6 (41)	4.03 (1.97-8.0)	7182 (52)

Values for  $C_{max,ss}$  and  $AUC_{24,ss}$  are presented as geometric means (%CV). Median values (range) are presented for  $T_{max}$ .

### 1.4.4. Additional Information

Detailed information for this compound may be found in the Single Reference Safety Document (SRSD), which for this study is the Investigator's Brochure of PF-06649751, and the prescribing information for L-Dopa (for example, Sinemet, Menesit, Madopar, Prolopa, or EC Dopar).

## **1.5. Rationale**

### **1.5.1. Study Rationale**

This study will evaluate the efficacy, safety, and tolerability of PF-06649751 as a potential novel therapeutic agent in subjects with Parkinson's disease.

PF-06649751 is a novel D1 and D5 specific dopamine partial agonist and has the potential to reduce OFF time in subjects with moderate to advanced Parkinson's disease who are experiencing significant OFF time despite their current dopaminergic therapy. Following an initial titration phase, which is intended to mitigate potential dopaminergic adverse events such as nausea and vomiting, fixed doses of PF-06649751 will be evaluated as adjunctive treatment with L-Dopa. The overall doses of PF-06649751 selected for this study were influenced by the aim to identify not only a minimally-effective dose but also characterize the maximum efficacious dose.

The study was initially limited to a maximum 15 week treatment period due to the available toxicological coverage. Subsequently, the nonclinical safety profile of PF-06649751 is considered to be adequately characterized to support progression into human clinical studies of 6 months or longer dosing duration for men and for women of non-childbearing potential.

Subjects who complete through Week 15 of the B7601003 study will have the option to enroll in an open label extension study (B7601017). If the pre-specified Inclusion/Exclusion criteria are met at Week 10 (screening), the subject may exit the current B7601003 study at Week 15 for continued treatment and follow-up under the extension study (B7601017), provided they remain eligible. Subjects not directly entering study B7601017 at Week 15 must complete the Week 17 and Week 19 Follow-up visits and must rescreen under the B7601017 protocol.

Based on reports of other dopaminergic drugs, the peak effect on OFF time has been observed after approximately 8 weeks of treatment.

The study population will include male subjects and female subjects of non-childbearing potential diagnosed with Parkinson's disease who experience motor fluctuations.

### **1.5.2. Dose Rationale**

PF-06649751 doses for this study are selected based on evidence of pharmacological activity from preclinical data and clinical studies in Parkinson's disease subjects. Based on experiments in MPTP monkeys, the human  $C_{\text{eff}}$  was established at 27.6 ng/mL. Based on the human Phase 1 pharmacokinetic data, a dose of 3 mg QD is expected to produce total plasma concentrations of PF-06649751 of at least 27.6 ng/mL, across the entire dosing interval, in Parkinson's disease subjects. Based on observed MDS-UPDRS Part III data from B7601009 and B7601005, a dose of 1 mg QD is likely to be a no- or minimal effect dose to evaluate the lower part of the dose-response curve. The top dose of 15 mg is chosen to establish safety and efficacy at a dose that is at the top part of the dose-response curve. The 7 mg QD dose will provide safety, tolerability and efficacy data at a dose lower than 15 mg dose to establish maximum efficacious dose with adequate safety in case of safety/tolerability issues at 15 mg

PF-06649751 dose group. The overall doses of PF-06649751 selected for this study were influenced by the aim to identify not only a minimally-effective dose but also characterize the maximum efficacious dose with adequate safety using the limited tablet strengths available (ie, 1 mg and 5 mg) as efficiently as possible without exceeding more than three tablets per dose. The selected dose range of 1 mg – 15 mg PF-06649751 QD is wide enough to facilitate appropriate dose selection for Phase 3 studies.

Even though MDS-UPDRS Part III scores from Phase 1b studies are used to drive dose selection, it should be noted that the primary endpoint for the current study is OFF time and not MDS-UPDRS Part III. Moreover, due to the uncontrolled, open-label study design, data from B7601005 may be subject to bias. These shortcomings in dose selection are addressed in the study design in order to achieve the primary aim of the study (establish dose response with OFF time).

- Confirm OFF time reduction at 15 mg dose (only) at the first interim analysis before initiating the dose ranging part of the study (see [DATA ANALYSIS/STATISTICAL METHODS](#)).
- Uncertainty in Phase 1b data is addressed by including doses (1 mg and 7 mg) bracketing the current preclinical estimate (~3 mg).

Based on the observed exposures from the 15 mg cohort in study B7601005, the top dose of 15 mg QD dose is expected to provide exposure ~2-3 fold lower than the stopping criteria from 15 week monkey toxicological study. Given the CYP3A4 mediated metabolism of PF-06649751, this provides a margin to allow for a possible increase in exposure of PF-06649751 when used together with weak inhibitors of CYP3A4. Patients receiving moderate to strong CYP3A4 inhibitors will be excluded from the study until further elucidation of the exact interaction magnitude in a drug-drug interaction study.

Therefore, based on the objectives to identify a minimum efficacious dose, maximum efficacious dose and evaluate dose-response, the following four PF-06649751 doses are proposed for the study along with a placebo: 1 mg QD, 3 mg QD, 7 mg QD and 15 mg QD PF-06649751.

### **1.5.3. Summary of Benefit-Risk Assessment**

The study is designed to assess the efficacy, safety, tolerability, and pharmacokinetics of PF-06649751 in subjects with Parkinson's disease. Based on the clinical safety data available to-date, PF-06649751 doses in this study do not pose any specific risk to study participants. The study will attempt to mitigate mild-to-moderate instances of nausea, emesis and abdominal discomfort seen in prior studies in healthy subjects and subjects with Parkinson's disease by slow dose escalation. Any potential risks will be further minimized by safety monitoring during the study and follow up for the subjects' well-being.

## 2. STUDY OBJECTIVES AND ENDPOINTS

### 2.1. Primary Objective

- To evaluate the effect on motor symptoms of PF-06649751 administered once daily as adjunctive treatment with stable doses of L-Dopa in Parkinson's disease.
- To determine the therapeutic window for motor symptom improvement of PF-06649751 administered once daily, ie, determining a dose, or a range of doses, for adequate control of motor symptoms.

### 2.2. Secondary Objectives

- To evaluate the dose-response on motor symptoms of PF-06649751 administered once daily in subjects with Parkinson's disease.
- To evaluate the safety and tolerability of PF-06649751 administered once daily in subjects with Parkinson's disease.
- To evaluate the effect of PF-06649751 administered once daily on dyskinesia in subjects with Parkinson's disease.

CCI

### 2.4. Endpoints

#### 2.4.1. Primary Endpoint (Efficacy)

- Change from baseline in daily OFF time (hours OFF time; based on patient reported Hauser diary) at Week 10 (Day 70; end of Period A).

#### 2.4.2. Secondary Endpoints (Efficacy; Evaluated during the entire double-blind period)

Change from baseline in:

- Daily OFF time (hours).
- Daily ON time with troublesome dyskinesia (hours).
- Daily ON time without troublesome dyskinesia (hours).

- MDS - Unified Parkinson's Disease Rating Scale (MDS-UPDRS) Part III.
- MDS-UPDRS Parts I, II, IV, and total score.

**2.4.2.1. Secondary Endpoints (Safety and Tolerability)**

- Adverse events.
- Clinical laboratory parameters.
- Vital signs.
- ECG parameters.
- Columbia Suicide Severity Rating Scale (C-SSRS).
- Questionnaire for Impulsive-Compulsive Disorders in Parkinson's Disease – Rating Scale (QUIP-RS).
- Physician Withdrawal Checklist (PWC-20).

CCI

### 3. STUDY DESIGN

[figure not shown]
#### 3.1. Study Overview

The study has a randomized, double-blind, placebo-controlled parallel group design. Approximately 198 subjects from approximately 60 centers in approximately 6 countries will be randomized to 5 treatment groups (15 mg QD, 7 mg QD, 3 mg QD, 1 mg QD, or placebo), initially in a 2:0:0:0:1 ratio of approximately 54 subjects (Cohort 1) followed by a 1:2:2:2:1 ratio of approximately 144 subjects (Cohort 2), using a central randomization system with randomization blocks stratified by region.

Each subject will participate in the study for approximately 25 weeks including up to a 45 day screening period, 15 week double-blind treatment period (comprising up to a 3 week titration, 2 week dose adjustment, 5 weeks of primary efficacy with adjunctive treatment to stable L-Dopa (Period A), and 5 weeks of maintenance with adjunctive treatment to stable L-Dopa (Period B)), and an approximately 28 day follow-up period.

The study design is illustrated in the figure below. For details on the dosing during the titration phase, see Section 5.5.1, **Titration of PF-06649751**.

Figure 1. Study Schematic

### 3.1.1. Screening

Screening evaluation will occur within 45 days prior to Day 0 (Randomization). Rescreening may be permitted after discussion with the study medical monitor. Screening procedures may split between multiple days/visits for feasibility and/or subject comfort; however individual procedures should not be split between multiple days/visits.

Subjects will document their symptoms (ON, OFF, ON with/without dyskinesia, ON with non-troublesome dyskinesia, ON with troublesome dyskinesia) in a patient diary (see Section 7.3.1 [OFF Time Diary \(Hauser Diary\)](#)).

- For Screening ON/OFF time concordance testing (see Section 7.1.7, [Concordance Testing and OFF Time Diary Training](#)), the subject must have at least 75% concordance with investigator (or qualified site staff/rater).
- For the final Inclusion/Exclusion criteria verification on Day 0 (Randomization) by the investigator, subjects must have  $\geq 2.5$  hours OFF time each day, collected over 3 consecutive days during the week prior to Day 0 (Randomization), with fewer than 4 errors or missing entries in diary data per day.

### 3.1.2. Double Blind Period

Eligible subjects will enter the 15 week double blind treatment phase, consisting of:

- Up to 3 week titration of PF-06649751 or placebo administered once daily to the randomized target dose ([Section 5.5.1](#)).
- 2 week stabilization period for dose adjustment after reaching the target dose with possible return to previous dose level after completion of the titration period. For subjects with intolerable adverse events, adjunct L-Dopa dose may subsequently be reduced after consultation with the Medical Monitor (see Section 5.5.1 [Titration of PF-06649751](#)).
- Period A (Primary Efficacy): a 5 week period of PF-06649751 or placebo administered once daily adjunctive to stable doses of L-Dopa ([Section 5.5.2](#)).
- Period B (Maintenance): a 5 week maintenance period of PF-06649751 or placebo administered once daily adjunctive to stable doses of L-Dopa ([Section 5.5.3](#)).

Subjects will return to the clinic at the end of Weeks 1, 2, 3, 4, 5, 10, 15, and 17. Weeks 2 and 3 may be conducted as phone visits, at the discretion of the investigator.

All other visits will be conducted as phone visits; as per Section 6.5 ([Unplanned Visits](#)), the investigator has the discretion to conduct an unplanned clinic visit if warranted for subject safety. For guidance on concomitant medications for Parkinson's disease and other disorders please see Section 5.8, [Concomitant Treatment\(s\)](#).

### **3.1.3. Follow-up Period**

A follow up visit two weeks after discontinuation of PF-06649751 or placebo will take place at Week 17 for subject safety. A follow up phone visit will occur approximately 28 days after discontinuation of PF-06649751 or placebo at Week 19 for subject safety assessment. For all subjects who have received at least 1 dose of investigational product (except a subject who withdraws consent), follow-up contact will be completed at least 28 calendar days, and up to 35 calendar days after the last administration of the investigational product.

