### **3.1.4. Open Label Extension Study**

Subjects who complete through Week 15 of the B7601003 study will have the option to enroll in an open label extension study (B7601017). If all specified Inclusion/Exclusion criteria are met at Week 10/Screening Visit (B7601017), the subject may exit the current B7601003 study at Week 15/Baseline Visit (B7601017) for continued treatment and follow-up under the open label extension study (B7601017), provided they remain eligible.

Subjects not directly entering study B7601017 at Week 15 must complete the Week 17 and Week 19 Follow-up visits as required per protocol.

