## **5.4. Investigational Product Supplies**

### **5.4.1. Dosage Form(s) and Packaging**

Blinded PF-06649751 and its matched placebo will be provided as tablets for oral administration. The 1 mg, 5 mg, and their matching placebos will be supplied in weekly blister cards. At each dispensing visit, subjects will receive sufficient quantity of investigational product (IP) to last until their next scheduled visit. Each blister card will be labeled according to local regulatory requirements.

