## 6.2. Study Period

For the study period described below, there is a +3 day visit window for scheduling of visits during Weeks 1, 2, and 3.

For Weeks 4-19, the visit window for scheduling visits will be  $\pm 3$  days.

**Study visit times are relative to Day 0 (Randomization), and not relative to when the previous visit actually occurred. The indicated visit windows are only intended to mitigate scheduling conflicts for study visits, and efforts should be made to return the subject to the correct timelines.**

For each visit, the following chronology of events should be adhered to, where possible:

- Patient Reported Outcome scales (ie, [CCI](#), [QUIP-RS](#), [CCI](#)): obtain prior to UPDRS.
- UPDRS Assessment: obtain prior to ECGs.
- ECGs: obtain prior to blood pressure and heart rate.
- Blood pressure/pulse rate: obtain prior to safety laboratory tests.

- Safety laboratory tests: obtain prior to pharmacokinetic (PK) blood.
- Pharmacokinetic blood specimens.
- Other procedures may be obtained before or after those listed above.

### 6.2.1. Randomization: Day 0

- Assessment of prior/concomitant medications.
- Review changes in medical history since screening visit.
- Review Inclusion and Exclusion criteria.
- Perform brief physical and neurological examination.
- Collect blood and urine for safety lab tests. Screening labs must have no clinically significant findings, as judged by the investigator, in order for the subject to be dosed with PF-06649751 or placebo.
- Urine drug screening in the form of a dipstick performed at the site.
- CCI [REDACTED]
- Collect Prolactin laboratory sample.
- Perform standard supine triplicate 12-lead electrocardiogram (ECG).
- Perform standard single supine and standing vitals (HR and blood pressure) and assess subject temperature to confirm no symptoms of fever.
- Perform the Columbia Suicidality Severity Rating Scale (C-SSRS) “Since last evaluation”.
- Collect and review OFF time diary while subject is present; confirm subject eligibility for OFF time has been met.
- Perform MDS-UPDRS I, II, III, and IV.
- CCI [REDACTED]
- CCI [REDACTED]
- CCI [REDACTED]

- CCI [REDACTED].
- CCI [REDACTED].
- Perform Questionnaire for Impulsive-Compulsive Disorders in Parkinson's Disease – Rating Scale (QUIP-RS).
- Perform Oral Symbol Digit Modality Test (SDMT).
- Perform Modified Clinical Global Impression - Severity (MCGI-S).
- CCI [REDACTED].
- Review and assess adverse events (AEs).

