- Register subject as Randomized in IWR system in order to obtain randomization number.
- Dispense Investigational Product. Subjects will begin PF-06649751 or placebo dosing the following morning (Day 1).
- Instruct subjects on continued daily dosing of PF-06649751 or placebo in accordance with randomized dose arm up-titration scheme (see [Table 2](#), Section 5.5.1, [Titration of PF-06649751](#)) and instruct subjects on proper dosing documentation.
- Instruct subjects on continued adjunct stable L-Dopa (open-label) administration.

#### 6.2.2. Dosing: Day 1 through Day 105

- Continued once daily dosing of PF-06649751 or placebo in accordance with randomized dose arm up-titration scheme (see [Table 2](#), Section 5.5.1, [Titration of PF-06649751](#)).
- Continued adjunct stable open-label L-Dopa administration (through Period B).

#### 6.2.3. Titration Period: Day 7

- Dosing compliance verification (Investigational product accountability and documentation) while subject is present to confirm reasons for missed/additional doses. **Based on blister card review and/or tablet count, any subject who is noted not to have taken at least 80% or has taken more than 120% of required doses at any scheduled visit during the study will be considered out of compliance and this must be recorded on the CRF and documented as a Medication Error on the CRF and the source documents.**
- Review and assess adverse events (AEs).
- Assessment of concomitant medications.

- Perform the Columbia Suicidality Severity Rating Scale (C-SSRS) “Since last evaluation”.
- Perform standard supine triplicate 12-lead electrocardiogram (ECG).
- Perform standard single supine and standing vitals (HR and blood pressure).
- Perform MDS-UPDRS Part III.
- Dispense OFF time diary, review instructions including requirement to wait until the next phone visit before completion of the diary.
- Dispense Investigational Product. Next immediate dose level of PF-06649751 or placebo will be taken the next morning.
- Instruct subjects on continued daily dosing of PF-06649751 or placebo in accordance with randomized dose arm up-titration scheme (see [Table 2](#), Section 5.5.1, [Titration of PF-06649751](#)).
- Instruct subjects on continued adjunct stable L-Dopa (open-label) administration.

#### 6.2.4. Titration Period: Day 14

In the case of a phone visit:

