#### **6.4. Follow-up Visit: Day 133 (Phone Visit)**

- Review and assess adverse events (AEs).

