It may be appropriate for the subject to return to the clinic for final safety assessments and to be questioned regarding their reason for withdrawal. At the early withdrawal visit, every effort must be made to complete the assessments as specified in the Early Termination Visit.

- Full physical and neurological examination, if there is a new or open AE or clinically significant abnormal physical finding from the last visit;
- Assessment of concomitant medications;
- Single supine and standing blood pressure and pulse rate measurements;
- Triplicate 12-lead ECG measurement;
- Columbia Suicidality Severity Rating Scale (C-SSRS) "Since last evaluation";
- Blood and urine specimens for safety laboratory;

- Blood sample for pharmacokinetic analysis;
- Review OFF time diary since dosing was stopped;
- MDS-UPDRS Part I, II, III, and IV;
- CCI [REDACTED];
- CCI [REDACTED];
- CCI [REDACTED];
- CCI [REDACTED];
- Perform Questionnaire for Impulsive-Compulsive Disorders in Parkinson's Disease – Rating Scale (QUIP-RS).
- CCI [REDACTED];
- Physician Withdrawal Checklist (PWC-20);
- CCI [REDACTED];

Lack of completion of all or any of the early termination procedures will not be viewed as protocol deviations so long as the subject's safety was preserved.

For all subjects (including Early Termination) who have received at least 1 dose of investigational product (except a subject who withdraws consent), follow-up contact will be completed at least 28 calendar days, and up to 35 calendar days after the last administration of the investigational product to capture any potential adverse events (see the Time Period for Collecting AE/SAE Information section) and to confirm appropriate contraception usage (see the Contraception section). Contact with the subject may be done via a phone call.

If the subject withdraws from the study, and also withdraws consent for disclosure of future information, no further evaluations should be performed, and no additional data should be collected. The sponsor may retain and continue to use any data collected before such withdrawal of consent.

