## **8.2. Reporting Period**

For SAEs, the active reporting period to Pfizer or its designated representative begins from the time that the subject provides informed consent, which is obtained prior to the subject's participation in the study, ie, prior to undergoing any study-related procedure and/or receiving investigational product, through and including 28 calendar days after the last administration of the investigational product. SAEs occurring to a subject after the active reporting period has ended should be reported to the sponsor if the investigator becomes aware of them; at a minimum, all SAEs that the investigator believes have at least a reasonable possibility of being related to investigational product are to be reported to the Sponsor.

AEs (serious and non-serious) should be recorded on the case report form (CRF) from the time the subject has taken at least 1 dose of investigational product through the subject's last visit.

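### The Week 19 call window (Day 133 ± 3, counted from Day 0) admits calls 25–27 days after a Day 105 last dose, short of the mandatory 28-day minimum

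*Protocol*

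**What the plan says.** Two rules govern the final follow-up contact.

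- **Counted from the last dose.** Section 3.1.3 places the Week 19 call roughly 28 days after stopping treatment. It then requires, for all dosed subjects who have not withdrawn consent, that "follow-up contact will be completed at least 28 calendar days, and up to 35 calendar days after the last administration of the investigational product". Section 6.6 repeats this, allows a phone call, and gives two purposes: capturing adverse events "and to confirm appropriate contraception usage (see the Contraception section").
- **Counted from randomization.** The Schedule of Activities puts the Week 19 call at Day 133 ± 3. Section 6.2 applies ± 3 days to all of Weeks 4–19 and adds: "Study visit times are relative to Day 0 (Randomization), and not relative to when the previous visit actually occurred".

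The planned end of treatment is given by the heading of Section 6.2.2, "Dosing: Day 1 through Day 105". The Week 15 visit has its own window of Day 105 ± 3. Section 5.4.1 says that at each dispensing visit "subjects will receive sufficient quantity of investigational product (IP) to last until their next scheduled visit". Section 6.4, the procedure list for the call, contains adverse event review and nothing else.

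On who receives the call, Section 3.1.4 says: "Subjects not directly entering study B7601017 at Week 15 must complete the Week 17 and Week 19 Follow-up visits as required per protocol".

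**The concern.** The 28-day minimum and the visit window start from different points, and nothing in the schedule reconciles them. The target day is the earliest day the minimum allows, yet the window extends three days before it. A site working from the Schedule of Activities and Section 6.4 can therefore make an on-schedule call that breaches 3.1.3 and 6.6, and neither place would alert it.

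This matters because Week 19 is the last scheduled contact. Under Section 8.2, adverse events go on the CRF "from the time the subject has taken at least 1 dose of investigational product through the subject's last visit", while active SAE reporting runs through day 28 after the last dose. Male contraception is also required for at least 28 days after the last dose (Sections 4.1 and 4.4.5). A call on Days 130–132 ends routine adverse event questioning before those periods are over, and it cannot confirm contraception for the whole of its required period.

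**Working it through.** **Inputs**

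- Required interval: 28 to 35 days after the last dose (3.1.3, 6.6).
- Call window: 133 − 3 = Day 130 to 133 + 3 = Day 136, seven days (Schedule of Activities, 6.2).
- Planned last dose: Day 105 (6.2.2).
- Week 15 visit window: 105 − 3 = Day 102 to 105 + 3 = Day 108 (Schedule of Activities).

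**Formula.** Interval = call day − last-dose day. A call complies if 28 ≤ interval ≤ 35.

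**The plan's own figure.** 133 − 105 = 28 days, which agrees with the approximate 28 days in 3.1.3.

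**Last dose on Day 105, as planned**

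- Day 130: 130 − 105 = 25, short by 3.
- Day 131: 131 − 105 = 26, short by 2.
- Day 132: 132 − 105 = 27, short by 1.
- Days 133 to 136: 28 to 31, compliant.

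So 3 of 7 window days fail and 4 comply. The compliant period is 105 + 28 = Day 133 to 105 + 35 = Day 140, so Days 137–140 satisfy the 28–35 day rule but lie outside the visit window.

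**Last dose moving with the Week 15 visit.** This is an assumption: the subject stops on the day of an early or late visit. The number of window days below the minimum is the last-dose day minus 102.

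| Last dose | Intervals over Days 130–136 | Compliant days | Interval at Day 133 |
|---|---|---|---|
| Day 102 | 28–34 | 7 of 7 | 31 |
| Day 103 | 27–33 | 6 of 7 | 30 |
| Day 104 | 26–32 | 5 of 7 | 29 |
| Day 105 | 25–31 | 4 of 7 | 28 |
| Day 106 | 24–30 | 3 of 7 | 27 |
| Day 107 | 23–29 | 2 of 7 | 26 |
| Day 108 | 22–28 | 1 of 7 (Day 136) | 25 |

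Across the table the shortest interval is 130 − 108 = 22 days and the longest is 136 − 102 = 34 days. The 35-day maximum is never at risk. At least one compliant day exists in every row.

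**The case against.** The best defence is that the protocol already settles the matter. The 28-day minimum stands in the same paragraph that introduces the Week 19 call, and 6.6 repeats it. The ± 3 window is a general tolerance that Section 6.2 says is meant only to ease scheduling conflicts, and a specific mandatory minimum should override it. An early call would not discharge the requirement, so a second contact would still be owed. On this view, the point asks only for an existing rule to be restated.

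The consequences are also limited:

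- SAE reporting runs to day 28 whatever the date of the call, and later SAEs that come to the investigator's attention are covered by 8.2.
- The contraception period is fixed by its own terms; the call only confirms it.
- SAP Section 3.5.1 uses an infinite lag for treatment-emergent events, so the timing of the call does not change attribution of recorded events.
- The mean single-dose half-life is at most 22.4 hours (Section 1.4.3), so 25 days is 25 × 24 / 22.4 ≈ 27 half-lives.
- The Week 17 clinic visit covers laboratory tests, ECG, C-SSRS and PWC-20, and PWC-20 is also done at Day 105.

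Finally, the worst figures need dosing on Days 106–108, beyond the heading of 6.2.2.

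Most of this stands, and it is why the point is minor. The two rules are compatible, the 28-day minimum still binds after an early call, and the Day 106–108 rows are conditional. It does not remove the mismatch in the planned case. With a Day 105 last dose, the schedule accepts three call days that a mandatory rule rejects, and no text removes the early side of the window for Week 19. Whether the gap is closed depends on the site noticing a rule found only in the design overview and the withdrawal section. The missing contraception check in 6.4 is weaker: 6.6 already requires it, and it would not be worth raising alone.

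**Conclusion.** The concern holds, at low severity. With dosing ending on Day 105 as planned, 3 of the 7 in-window call days fall 1–3 days below the required 28. If dosing continues to a late Week 15 visit, even an on-target call is too early, by 1 day (last dose Day 106) to 3 days (Day 108). If dosing stops on Day 102, all seven days comply.

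Only the lower bound is affected. The practical effect is avoidable deviations or repeat calls and, where the site does not notice, a slightly early end to routine adverse event questioning. Subjects who enter the extension directly at Week 15 have no Week 19 call. No efficacy analysis or decision rule changes. How often sites would call early cannot be judged from the documents.

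**What to change.** In the Schedule of Activities, Section 6.2 and Section 6.4, define the Week 19 call as taking place 28 to 35 days after the actual last dose. State that this replaces the Day 0 window for this contact. For a Day 105 last dose the result is Day 133 −0/+7, that is Days 133–140. In the same edit, add the contraception confirmation from 6.6 to the list in 6.4 so that the site has one complete checklist.

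The cost is protocol wording. No visit is added. After a Day 105 last dose the call could take place at most 140 − 136 = 4 days later than the present window allows.
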